Overview: This four-year multi-site site-level randomized stepped wedge trial will test the effectiveness of the intervention to improve adherence and outcomes, and will formatively evaluate and refine the implementation process. This is a randomized stepped-wedge study, modified to allow stratification by clopidogrel adherence. We will randomize 16 VA PCI sites to the multi-faceted intervention through 4 roll-out phases. We will implement the intervention at 4 sites during each roll-out and incorporate a 6-month delay between the start of each roll-out. The rest of the PCI sites that are not randomized will serve as usual care control group. At each site, we will enroll patients over a 6-month period and follow them for 12 months following PCI. The multi-faceted intervention will adapt elements of prior successful intervention and will include the following core components: development of a software application integrated within CART-CL that assessed whether patients fill their clopidogrel prescription at hospital discharge, collaboration between cath lab clinicians and inpatient/outpatient pharmacy teams, patient education, and tele-monitoring via IVR technology.

A. Outcome Measure(s):

Initial outcomes will assess understanding current practices as VA PCI facilities to enhance adherence to clopidogrel. We will then assess barriers and facilitators to intervention implementation during each roll-out phase through semi-structured interviews and incorporate lessons learned from each roll-out phase into subsequent roll-out phases.

The primary outcomes of the study include the proportion of patients whose clopidogrel prescription is filled at hospital discharge following the PCI stent placement as well as the proportion of patients who are adherent based on the pharmacy refill data in the year after hospital discharge. Secondary outcomes include hospitalizations for bleeding, myocardial infarction, stroke, and mortality. Additionally, data about the costs of the intervention will be collected to assess the cost-effectiveness of the intervention.

B. Description of Population to be Enrolled:

Setting, sites, and patients:

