We will obtain basic demographic data (including phone number), co-morbidities, PCI procedural details as well as the date of initial clopidogrel fill with and the number of days of pills supplied from CART-CL. We have obtained CART-CL data as part of our pilot intervention to improve clopidogrel adherence, demonstrating technical feasibility. Next, we will obtain data on subsequent clopidogrel refills from the CDW, including the date of refill, the number of pills supplied and the prescription number. The pharmacy data in the CDW is refreshed on a daily basis and will be linked to the CART data (Figure 7). The data will be compiled and analyzed in Denver and/or Nashville and will be in a secured database that will be saved on a VA secured server maintained behind the VA firewall. Access to the database and study data will be limited to research staff. Only personnel who are qualified, trained, and IRB-approved in appropriate behavior for the privacy of each patient will be viewing the data. Then, we will be able to use these data to trigger the IVR calls based on when a clopidogrel prescription is due to be refilled and to notify the PACT team about patients who have not refilled clopidogrel. This is consistent with our processes in the pilot intervention to improve clopidogrel adherence as well as in our other prior IVR studies.

Figure 7: Overview of Data Sources and Use

We will work with site champions to identify and interview key clinicians/personnel involved in the delivery of the intervention and the interviews will be designed to understand barriers to and facilitators of intervention implementation. In addition, we will interview patients to obtain feedback regarding the IVR calls as well as other aspects of the intervention.

We will collect data on costs in two main categories: direct medical costs and intervention costs. To calculate medical costs for each patient we will collect Decision Support System (DSS) data for all patients for the one year following the receipt of the stent. We will collect DSS data for outpatient care in primary care, cardiology, pharmacy, and geriatric clinics; and for emergency department use, hospitalization, and medications. For hospitalizations we will report costs for all cause hospitalizations as well as hospitalizations for cardiovascular-related conditions. Similarly for medications, we will estimate costs for all medications and for cardiovascular-related medications.

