The economic analysis will weigh the benefits of the intervention in terms of patient survival and quality of life against the cost implications of providing the interventions. We will do this through a cost effectiveness analysis (CEA). The CEA will take the perspective of the VA and the time horizon will be the 12 month period following stent placement. For the intervention compared to usual care we will calculate incremental cost effectiveness ratio (ICER) and related statistics. The ICER is estimated as $ICER = (C_1 - C_0) / (QALY_1 - QALY_0)$ where C_1 and C_0 are average cost over 1 year for patients in the INT and UC groups, respectively, and $QALY_1$ and $QALY_0$ are mean quality adjusted years of survival over that year for the respective groups. Below we describe data sources and methods for deriving these estimates.

To estimate the cost of the intervention we will use micro-cost techniques. The cost of developing and tailoring the email and IVR systems will be derived from logs of the time, salaries and benefits of personnel devoted to those tasks. The costs of inpatient pharmacists will be derived from direct observations. We will randomly selected times and study sites to conduct brief interviews with inpatient pharmacists to assess typical time related to delivering the intervention. Estimates of PACT team-member time will be assessed similarly.

To estimate mean QALYs for the intervention and usual care groups requires data on survival time over the 12 months post stent for every patient, and a measure of the quality of life for each patient over those 12 months. Data on survival will come from CDW vital statistics file.

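### Outpatient cost is limited to four clinic types without a stated reason, although the cost-effectiveness analysis takes the VA perspective, so C1 - C0 may differ from the VA's incremental cost

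*Protocol*

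**What the plan says.** Protocol section IV.F (economic analysis) sets the frame: "The CEA will take the perspective of the VA and the time horizon will be the 12 month period following stent placement". The ICER numerator is C1 - C0, where the two terms "are average cost over 1 year for patients in the INT and UC groups".

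Section IV.D says what is counted: "We will collect data on costs in two main categories: direct medical costs and intervention costs". For medical cost, DSS data are taken for every patient for one year after the stent. The outpatient part reads "We will collect DSS data for outpatient care in primary care, cardiology, pharmacy, and geriatric clinics", followed by "and for emergency department use, hospitalization, and medications". Two of these categories are explicitly comprehensive: "For hospitalizations we will report costs for all cause hospitalizations as well as hospitalizations for cardiovascular-related conditions", and medications are likewise costed both in total and for the cardiovascular subset. Outpatient care has no corresponding all-care total.

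Section IV.A lists the events of interest: "Secondary outcomes include hospitalizations for bleeding, myocardial infarction, stroke, and mortality". Section I hypothesizes that the intervention reduces them.

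On intervention cost, section IV.F says: "The cost of developing and tailoring the email and IVR systems will be derived from logs of the time, salaries and benefits of personnel". It gives no denominator for that cost. The SAP addendum does not mention costs.

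**The concern.** A VA-perspective analysis should count what the VA spends on these patients during the year. The outpatient list names four clinic types, has no wording that makes them examples, and gives no reason for stopping there. Specialist follow-up that a bleed or a stroke may generate, such as neurology, rehabilitation or gastroenterology visits, falls outside it.

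A cost left out of both groups equally would cancel from C1 - C0. Here the omitted follow-up is tied to events that the trial expects to differ between groups, so the plan cannot take cancellation for granted. The one-year QALY difference that divides C1 - C0 may well be small, in which case a modest cost error becomes a large change in the ICER and in the acceptability curves planned in section IV.F.

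**Working it through.** **What can be reproduced.** The documents state no cost, event rate, QALY difference or ICER, so there is no figure to reproduce. The check compares the stated scope with the stated perspective, then illustrates size with assumed inputs.

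**Scope by category (Protocol section IV.D)**

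| Category | Scope in the plan |
|---|---|
| Hospitalization | All-cause, plus cardiovascular subset |
| Medications | All, plus cardiovascular subset |
| Emergency department | Included, no restriction stated |
| Outpatient clinics | Four named types only |

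Only outpatient care is restricted. The acute cost of a bleed, MI or stroke is captured, because the non-fatal events are themselves defined as hospitalizations. Follow-up in primary care or cardiology is captured too. What is missed is VA outpatient care in any other clinic.

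**Size of the omission.** Let r1 and r0 be the event risks in the intervention and usual-care groups, and k the omitted outpatient cost per event. Considering event-driven use only:

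- Planned C1 - C0 minus the VA's C1 - C0 = -(r1 - r0) x k.
- Fewer events under the intervention: the plan overstates incremental cost. More events: it understates it.
- r1 = r0: the error is $0.

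Absolute error per patient, with both inputs assumed:

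| Risk difference | k = $1,000 | k = $3,000 | k = $10,000 |
|---|---|---|---|
| 0 | $0 | $0 | $0 |
| 0.5 points | $5 | $15 | $50 |
| 1 point | $10 | $30 | $100 |
| 2 points | $20 | $60 | $200 |

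**Effect on the ICER.** Shift = cost error / QALY difference. With an assumed QALY difference of 0.002 to 0.02:

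- $10 error: 10 / 0.002 = $5,000 down to 10 / 0.02 = $500 per QALY.
- $50 error: 50 / 0.002 = $25,000 down to 50 / 0.02 = $2,500 per QALY.

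**Development cost (reporting point only).** Per-patient cost = D / N. The documents offer three possible values of N: 16 x 90 = 1,440 (section I); up to 2,500 (section IV.C, Aim 2 overview); and more than 10,000 stented PCI patients in FY10 (section IV.B). The last is not a count of eligible patients, because the Aim 2 setting text then excludes those discharged to facilities that manage their medications. For an assumed D of $200,000:

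- 200,000 / 1,440 = $139
- 200,000 / 2,500 = $80
- 200,000 / 10,000 = $20

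The ratio to the 10,000 base is 10,000 / 1,440 = 6.9 or 10,000 / 2,500 = 4. D is not given, so this shows only that the choice of base needs stating.

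**The case against.** The strongest reply is that the main cost channels are already counted: emergency care, all hospital stays, all medications, and the clinics where most routine post-PCI follow-up might be expected. What remains is specialist outpatient follow-up, which biases C1 - C0 only through a between-group difference in its use, and any such difference has to be assumed. All of this stands, and it limits the point to a possible bias of unknown size and direction. It does not explain why outpatient care alone is restricted, and equal use cannot be presumed for care that follows events the intervention is meant to change.

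A reader might infer more than the documents support:

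- *That most VA outpatient care is left out.* The documents give no list of VA clinics and no cost shares, so this cannot be checked.
- *That the cost of bleeding and stroke is missing.* The acute cost is counted.
- *That one-off development cost is wrongly loaded onto trial patients.* Section IV.F says how that cost is measured, not how it is spread. Including a start-up cost that the VA bears is legitimate if declared. The item also covers tailoring, which could recur at each new site. Sections II and IV.C describe the software application and calls as already used in the pilot, so the new development cost may be small.
- *That the ICER is defined for a national roll-out.* It is defined for this study's two groups; wider use is an aspiration.

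**Conclusion.** The outpatient cost scope is narrower than the stated VA perspective, without justification, and the SAP addendum does not repair it. C1 - C0 may therefore differ from the VA's incremental cost if the intervention changes bleeding or stroke, or otherwise changes use of the omitted clinics. It does not follow that C1 - C0 is wrong. The illustrative $0 to $200 per patient rests wholly on assumed risk differences (0 to 2 points) and assumed omitted cost per event ($1,000 to $10,000); the documents fix neither size nor direction. The matter concerns Aim 6 only and leaves the adherence and clinical outcome analyses untouched. It is worth correcting because the correction is cheap.

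The missing allocation base for development cost is a gap in reporting, not an error in the plan.

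**What to change.** 1. In section IV.D, and in the definition of C1 and C0 in section IV.F, use all VA outpatient cost recorded in DSS for the 12 months after the stent, for every patient in both groups. Report the four-clinic subset as a secondary breakdown, under a label that does not call it cardiovascular, since it includes primary care and geriatrics.
2. As a minor addition, state the number of patients over which development cost is spread and show the ICER with and without that cost. Keep recurring site tailoring separate from one-off development.

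**Cost.** DSS data are already to be collected for all patients, so the first change is a wider pull from the same source; the documents do not say how the extract is built, so it may have to be rerun. Unrelated visits will make total cost somewhat noisier, and the planned bootstrap will show this in the ICER's uncertainty. The second change needs one extra table, drawn from the personnel logs already planned and split between development and tailoring.

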Therefore, our main objective is to conduct a type 1 hybrid effectiveness/implementation study to test the effectiveness of a successfully-piloted, evidence-based, multi-faceted intervention to improve patient adherence to clopidogrel following PCI. The proposed study will test the hypothesis that a successfully-piloted, evidence-based, multi-faceted intervention targeting veterans following PCI procedure improves adherence to clopidogrel, reduces bleeding, myocardial infarction, stroke, and mortality among these patients, and is cost-effective. The proposed intervention will be based on the Chronic Care Model and will build on our pilot work as well as will leverage the VA's CART-CL, a uniform cath lab procedure reporting tool at all VA cath labs. The study will be evaluated using the RE-AIM framework consisting of the following components, reach, effectiveness, adoption, implementation and maintenance. The intervention will adapt elements of prior successful intervention, including patient education, collaboration between cath lab clinicians and inpatient/outpatient pharmacy teams, and tele-monitoring via interactive voice response (IVR) technology. This type I hybrid effectiveness/implementation study will be tested at 16 sites randomized to intervention with an average of 90 patients per site per 6 month period versus usual care.

Specific Aims:

1. To evaluate current practices at VA PCI facilities (n=16) to enhance adherence to clopidogrel, both at hospital discharge and during longitudinal follow-up.
2. To implement the multi-faceted intervention at 16 total sites through 4 roll-out phases (4 sites during each roll-out) in a randomized stepped wedge trial design.

3. To assess barriers and facilitators to intervention implementation during each roll-out phase through semi-structured interviews and incorporate lessons learned from each roll-out phase into subsequent roll-out phases.
4. To determine the effectiveness of a successfully-piloted, evidence-based, multi-faceted intervention versus usual care for improving clopidogrel filling at hospital discharge and adherence to clopidogrel (primary outcomes).
5. To determine the effectiveness of a successfully-piloted, evidence-based, multi-faceted intervention versus usual care for reducing the combined cardiovascular endpoints of bleeding, myocardial infarction, stroke, and mortality (secondary outcomes).

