Although we hope the randomized step-wedge design of the trial will lead to treatment groups that are balanced on observed covariates at baseline, we recognize that some imbalances may nevertheless occur and multivariable models maybe necessary to account for these imbalances. To assess differences in costs we will use analytic models that account for the skewed nature of cost data, and we will pay special attention to the possible biases caused by heteroscedastic error terms across INT and UC groups (44-45). Because QoL data are bounded by 0 and 1, we use beta models to estimate differences in QALYs by treatment group (46). We will use bootstrapping to estimate the uncertainty of the ICER. If the INT group is found to have better outcomes but at higher mean costs than UC, we will produce cost effectiveness acceptability curves to depict the probability that the intervention would be cost effective at various levels of willingness to pay for an additional QALY (47).

G. Summarize Knowledge to be Gained:

This study will refine the current state of knowledge on improving medication adherence in multiple ways. First, it combines multiple interventions that have been separately shown to be effective in improving medication adherence and addresses causes of clopidogrel non-adherence identified by patients. Second, the intervention focuses on a novel setting (i.e., patients discharged following PCI and transitioning to outpatient care) in contrast to prior adherence interventions that have focused only on patients with stable chronic diseases (e.g., hypertension). Third, the targeted medication in this study has demonstrated short-term benefits and where non-adherence can have immediate adverse outcomes (e.g., stent thrombosis with discontinuation of clopidogrel). Fourth, the study utilizes existing

resources (i.e., cardiac data systems integrated with the VA electronic health record, VA pharmacists and patient-aligned care teams) to implement the intervention, improving the feasibility of broader implementation. Finally, this study is being conducted as a type I hybrid implementation study and therefore includes extensive study of the implementation process, which will yield both contributions to implementation science and facilitate wider dissemination if the intervention is found to be effective.

H. References:

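### Acceptability curves are planned for one of the four cost-effectiveness quadrants; in the others the only named joint measure of uncertainty is a bootstrapped ICER, which can be uninterpretable if the 12-month QALY difference is small relative to its standard error.

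*Protocol*

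**What the plan says.** Everything on this point is in the economic part of the protocol's section IV.F, Data Analysis Plan. The comparison of INT with UC is summarised by a ratio: "we will calculate incremental cost effectiveness ratio (ICER) and related statistics". The ICER is the difference in mean one-year cost divided by the difference in mean QALYs, and "the time horizon will be the 12 month period following stent placement". The related statistics are not named.

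Two component analyses are planned. For costs: "To assess differences in costs we will use analytic models that account for the skewed nature of cost data". For QALYs: "we use beta models to estimate differences in QALYs by treatment group".

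Joint uncertainty is covered in two sentences. The first is "We will use bootstrapping to estimate the uncertainty of the ICER". The second is conditional: "If the INT group is found to have better outcomes but at higher mean costs than UC, we will produce cost effectiveness acceptability curves", to show the probability of cost-effectiveness at various levels of willingness to pay.

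The plan does not state the type of bootstrap interval, the resampling unit, how ratios from different quadrants are handled, or any willingness-to-pay value. Net monetary benefit is not mentioned. The SAP addendum describes bootstrap inference for adherence and, by the same methods, survival differences. It adds nothing on the economic analysis.

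**The concern.** Whether a decision-uncertainty display appears depends on the result. The case named is better and costlier (the north-east quadrant of the cost-effectiveness plane). A better-and-cheaper estimate has no planned curve, and that is where a reader is most likely to take dominance as settled.

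Without a curve, the named joint measure is the bootstrapped ICER. A ratio whose denominator may be zero behaves badly. Bootstrap values become very large in both directions, and the sign loses its meaning. A negative ratio arises both when the intervention dominates and when it is dominated. A positive ratio arises both from better-and-costlier and from worse-and-cheaper. Sorting such values mixes opposite conclusions.

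Cost-effectiveness is Specific Aim 6 and part of the study's main hypothesis, so a poorly summarised result would weaken a named deliverable.

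**Working it through.** The documents give no expected QALY difference, cost difference, standard error or willingness to pay, so there is no plan figure to reproduce. Everything below is illustrative.

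**Main scenario (assumed).** QALY difference dQ ~ N(0.005, SE 0.008); cost difference dC ~ N(-100, SE 900) dollars; the two independent.

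1. *Quadrants.* P(dQ > 0) = Φ(0.005/0.008) = Φ(0.625) = 0.734. P(dC > 0) = Φ(-100/900) = Φ(-0.111) = 0.456.
   - Better and costlier: 0.734 × 0.456 = 0.335
   - Better and cheaper: 0.734 × 0.544 = 0.40
   - Worse and costlier: 0.266 × 0.456 = 0.121
   - Worse and cheaper: 0.266 × 0.544 = 0.145

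2. *ICER.* Simulating dC/dQ gives 2.5th and 97.5th percentiles of about -1.2 and +1.2 million per QALY. A Fieller interval is bounded only if |dQ| > 1.96 × 0.008 = 0.0157. Since 0.005 is below that, it is unbounded.

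3. *Does the plan call for a curve?* The point estimate is better and cheaper, so the stated condition is not met.

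4. *What a curve and net monetary benefit (NMB) would show.* NMB = λ·dQ - dC, with variance λ²·SE(dQ)² + SE(dC)².
   - λ = 50,000: mean 250 + 100 = 350; SE = √(400² + 900²) = 985; P(NMB > 0) = Φ(350/985) = 0.64.
   - λ = 100,000: mean 500 + 100 = 600; SE = √(800² + 900²) = 1,204; P(NMB > 0) = Φ(600/1,204) = 0.69; 95% interval 600 ± 1.96 × 1,204 = about -1,760 to +2,960.

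**Sensitivity to the assumed QALY difference** (other inputs unchanged):

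| dQ (SE 0.008) | Draws with dQ < 0 | ICER percentiles | Fieller bounded? |
|---|---|---|---|
| 0.005 | about 27% | about -1.2 to +1.2 million | no |
| 0.02 | under 1% | about -148,000 to +126,000 | yes |
| 0.03 | under 0.1% | about -73,000 to +64,000 | yes |

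**How large must the difference be?** The protocol expects "16 sites randomized to intervention with an average of 90 patients per site per 6 month period", that is 16 × 90 = 1,440 intervention patients. Assume a QALY SD of 0.20, an equal UC group and no design effect. Then SE(dQ) = 0.20 × √(2/1,440) = 0.0075, and the Fieller interval is unbounded unless the estimated |dQ| exceeds 1.96 × 0.0075 = about 0.015. This threshold runs from about 0.005 to 0.031 over assumed SDs of 0.10 to 0.30, 1,440 or 2,500 intervention patients, a UC group of equal size or 5,000, and a design effect of 1 or 2.

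With the base-case SE, a true dQ of 0.005, a true dC of +500 dollars and an assumed cost SD of 30,000 dollars, 50.5% of simulated estimates fall in the better-and-costlier quadrant. Read on point estimates, the curve condition would be met in about half of such trials.

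**The case against.** The strongest reply is that the text is looser than a critic might make it. It says if, not only if, and it does not forbid curves elsewhere. The word found could refer to statistical significance rather than to point estimates. No percentile interval is named, and a joint bootstrap also yields a scatter and quadrant proportions. The separate cost and QALY models would ordinarily carry their own uncertainty, and the related statistics are open-ended. In the better-and-costlier case the plan already delivers the right display.

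All of that stands, and it rules out stronger inferences. A reader might conclude that Aim 6 must end either in a meaningless interval or in an unqualified claim of dominance, or that the ICER is the only expression of uncertainty planned. The documents support neither. A reader might also infer that the 12-month QALY difference will be near zero. No figure in the documents says so, and at 0.02 or 0.03 (SE 0.008) the problem with the ratio largely disappears. The no-curve result in the main scenario also turns on the assumed sign of the cost difference. At +100 dollars the quadrant shares are similar and the curve would be drawn.

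What survives is narrower. No joint summary is promised outside one quadrant beyond the bootstrapped ratio, and separate intervals for cost and QALYs do not give a probability of cost-effectiveness. Reading found as significant would make the condition stricter and would still leave it dependent on the result.

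The protocol also names no source for the quality-of-life measure that its QALYs require. That is a larger gap, but it does not make this rule sound.

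**Conclusion.** The concern holds as a conditional one. Acceptability curves are planned for one result pattern, and no curve or net-benefit summary is planned for the other three. The remaining joint measure can be uninterpretable if the QALY difference is small relative to its standard error. The ±1.2 million range and the 0.69 probability rest entirely on the assumed dQ of 0.005 (SE 0.008), dC of -100 (SE 900) and independence. They show what could happen and do not forecast this trial's result. The point is a low-cost improvement to a non-primary aim and does not touch the adherence or clinical outcomes.

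**What to change.** Replace the conditional sentence in the economic part of section IV.F with wording such as: *In every case, whatever the quadrant of the point estimate, we will report the bootstrap scatter on the cost-effectiveness plane, the acceptability curve, and incremental net monetary benefit with 95% confidence intervals at stated willingness-to-pay values, keeping each patient's cost and QALY together in the bootstrap.* The willingness-to-pay values should be fixed in advance. The cost is slightly more reporting.

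Separately, the bootstrap should respect the clustering of patients within sites, which the same section already models for the primary analysis. The resampling unit is not stated, and with 16 intervention sites drawn from strata, site-level resampling is an analysis choice of its own. It needs its own specification and should not be treated as part of this wording change.
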